8.3.2 Time Period and Frequency for Collecting AE and SAE Information

Immediate Post-immunization Observation Period

Participants enrolled in the nirsevimab group will be kept under observation for 30 minutes after immunization to ensure their safety. The post-immunization observation should be documented in the source document.

Non-serious Adverse Events

Non-serious adverse events will be collected from dosing/randomization (D01) until 30 days after immunization, ie, D31.

The intensity grading scale for non-serious adverse events is presented in Appendix 10.2.5.1.

Medically Attended Adverse Events (MAAEs)

MAAEs will be collected from dosing/randomization (D01) to D366 phone call.

Adverse Events of Special Interest (AESIs)

AESIs will be collected from dosing/randomization (D01) to D366 phone call

See Section 8.3.7 for the list of AESIs.

SAEs

Information on SAEs will be collected and assessed throughout the study, from dosing/randomization (D01) until 12 months after immunization (D366) for all participants.

Information on related SAEs will be collected and assessed from D366 until D731 post-dosing/randomization for UK reconsented participants. Refer to Section 8.3.1 for the exemption of reporting LRTI hospitalizations as SAEs.

It is to be noted that, since this study is seeking real-world data, part of the participants' safety data will be collected retrospectively by the Investigator or designee. This means that, following the initial capture of information in the eDiary/memory aid by the parents or LARs, the Investigator or designee will be seeking additional or missing participant data from the medical facility where the medical visit or the hospitalization occurred to complete the corresponding eCRF.

All SAEs will be recorded and reported to the Sponsor or designee immediately and under no circumstance should this exceed 24 hours, as indicated in Appendix 10.2. The investigator will submit any updated SAE data to the Sponsor within 24 hours of it being available.

Investigators are not obligated to actively seek information on AEs or SAEs after conclusion of the study participation. However, if the investigator learns of any SAE, including a death, at any time after a participant has been discharged from the study, and he/she considers the event to be reasonably related to the study intervention or study participation, the investigator must promptly notify the Sponsor.

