9.4.5 Safety Analysis

Safety endpoints will be analyzed based on the SafAS defined in Section 9.3. Safety of nirsevimab will be assessed by the occurrence of immediate AEs, non-serious AEs within 30 days post-dosing/randomization, and MAAEs, SAEs, and AESIs following 12 months post-dosing/randomization for all participants, related SAEs from D366 to D731 for UK reconsented participants. All AEs will be coded by MedDRA system organ class and preferred term. The type, incidence, and severity will be summarized by treatment group. Relationship to nirsevimab will also be summarized.

In addition, all AEs (including immediate AEs, non-serious AEs within 30 days post-dosing/randomization, and MAAEs, SAEs and AESIs) in neonates < 28 days of age at randomization will be summarized.

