6.1. General Principles

All data processing, summarization and analyses will be performed using Fortrea's SAS Environment / Version 9.4 (or later) of the SAS® statistical software package.

The default summary statistics for quantitative variables will be the number of observations (n), mean, standard deviation (SD), median, minimum (min) and maximum (max), for those participants with data.

For qualitative variables, the number (n) and percentage (%) of participants with non-missing data per category will be the default summary presentation, and where appropriate and present, the number of missing values as a "Missing" category. Number of participants in the analysis population will be used as denominator for percentages calculation, unless otherwise stated in TFLs mock shell(s).

All statistical comparisons will be made using two sided tests at the $\alpha=0.05$ significance level unless specifically otherwise stated. All null hypotheses will be of no treatment difference. All alternative hypotheses will be two-sided.

Specifications for table, figure and data listing formats can be found in the TFL shells specifications for this study. Please refer to "2. General Format Guidelines" section within TFL shells for more details on presentation of results.

All analyses in the SAP will be carried out for all countries combined and as subgroup analyses by country.

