6.6.2.2. Tipping-Point Analysis

Due to the open-label nature of the study, an excess of withdrawals might be observed in the no intervention group and be translated into a biased estimator when assuming the non-informative censoring hypothesis.

In order to test this hypothesis, a tipping point analysis^{8,9,10} will be performed to assess the impact of imputating missing data under a various range of hypotheses.

1. In order to perform the tipping point analysis, data will be imputed for all participants with missing data, (ie who discontinued the study, or with a RSV test equals to missing or Not Done) from both groups, several scenarios will be evaluated:
 - a. Best case scenario: no RSV LRTI hospitalization among the missing data in nirsevimab group whereas all missing data in the no intervention group will be imputed as RSV LRTI hospitalization.
 - b. Worst case scenario: all missing data in nirsevimab group will be imputed as RSV LRTI hospitalization whereas no missing data in the no intervention group will be imputed as RSV LRTI hospitalization.
 - c. The number of RSV LRTI hospitalizations imputed in each arm will be incremented from 0% (complete case analysis with no RSV LRTI hospitalization imputed in any arm), by 10%, to the total number of missing data in each arm. Remaining participants with missing data (from 90% of total number of missing data to 0%) will be then imputed as having no RSV LRTI hospitalizations.
2. For each combination:
 - a. Person-months will be imputed in both treatment groups using the overall distribution of person-months in the respective group for non-missing participants. The following values will be considered and evaluated as different scenarios: minimum value, Q1, Q2, Q3 and maximum value.
 - b. Corresponding Incidence Rates will be imputed in each treatment arm.
 - c. For non aggregated rows, Efficacy for participants with missing data will be provided

$$\text{Eff}_{\text{miss}} = 100 \times \left(1 - \frac{\text{Incidence Rate Miss Nirsevimab}}{\text{Incidence Rate Miss No Intervention}} \right) = 100 \times \left(1 - \frac{\text{IRN}_{\text{Miss}}}{\text{IRC}_{\text{Miss}}} \right)$$

- d. For non aggregated rows, Overall Efficacy will also be computed with its 2-sided 95% Confidence Interval (described by Breslow and Day as for primary analysis) and corresponding p-value

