6.7.2.2. Analyses

Adverse events will be summarized by default descriptive summary statistics for categorical variables for the SafAS by treatment group and overall as follows:

- An overview of TEAEs (#) including the number and percentage of participants with at least one of each mentioned TEAE type provided with 95% Clopper-Pearson confidence interval:
 - Any TEAE
 - Leading to discontinuation of study
 - Leading to death
 - Grade 1 severity
 - Grade 2 severity
 - Grade 3 severity
 - Any study treatment related TEAE
 - Leading to discontinuation of study
 - Leading to death
 - Grade 1 severity
 - Grade 2 severity
 - Grade 3 severity
 - Any serious TEAE
 - Leading to discontinuation of study
 - Leading to death
 - Any serious study treatment related TEAE
 - Leading to discontinuation of study
 - Leading to death
 - Non-serious TEAEs until 30 days after Day 1
 - Leading to discontinuation of study
 - Grade 1 severity
 - Grade 2 severity
 - Grade 3 severity
 - Any immediate TEAEs reported in the 30 minutes after immunization
 - Leading to discontinuation of study
 - Leading to death

- Grade 1 severity
 - Grade 2 severity
 - Grade 3 severity
 - Medically-attended TEAEs
 - Leading to discontinuation of study
 - Leading to death
 - Grade 1 severity
 - Grade 2 severity
 - Grade 3 severity
 - TEAEs of Special Interest
 - Leading to discontinuation of study
 - Leading to death
 - Grade 1 severity
 - Grade 2 severity
 - Grade 3 severity
- The number and percentage of participants reporting each TEAE and the number of events as well as 95% Clopper-Pearson confidence interval will be summarized by SOC and PT for the following types of TEAEs:
 - Non-serious TEAEs through Day 31 post-dosing/randomization (*)
 - Immediate TEAEs reported in the 30 minutes post-dosing/ randomization (*)
 - Medically-attended TEAEs (*) (#)
 - TEAEs of Special Interest (*) (#)
 - TEAEs Leading to Death
 - TEAEs by Maximum Intensity (*) (#)
 - TEAEs by Relationship to Treatment (*) (#)
 - Study Treatment related TEAEs Leading to Death (*)
 - Serious TEAEs (*) (#)
 - Study Treatment Related Serious TEAEs (#)
 - Study Treatment Related TEAEs (*) (#)
- The number and percentage of participants who died will be summarized by the primary cause of death

All AE tables mentioned above will also be repeated for the following subgroups:

- ✓ By country
- ✓ By weight group (< 2.5 kg, < 5 kg, ≥ 5 kg)
- ✓ By age group (neonate participants, randomization stratification)

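### 12-month SAEs, MAAEs and AESIs are reported only as crude percentages of the safety set, so unobserved infants count as event-free; the pooled column also halves immediate and related AE rates

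*Protocol*

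**What the plan says.** Protocol 9.4.5 sets the general plan: "The type, incidence, and severity will be summarized by treatment group". The detail is in the SAP.

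- **Columns.** SAP 6.7.2.2 has AEs "summarized by default descriptive summary statistics for categorical variables for the SafAS by treatment group and overall".
- **Statistic.** The overview gives the "number and percentage of participants with at least one of each mentioned TEAE type provided with 95% Clopper-Pearson confidence interval". The tables by SOC and PT give "The number and percentage of participants reporting each TEAE and the number of events as well as 95% Clopper-Pearson confidence interval". No person-time or time-to-first-event measure for AEs appears in SAP 6.7.
- **Denominator.** SAP 6.1 states "Number of participants in the analysis population will be used as denominator for percentages calculation", unless the table shells say otherwise. The shells are not among the documents.
- **Safety set.** SAP 4.4 takes everyone who received nirsevimab plus every control who did not receive it inadvertently. It requires no safety contact.
- **Observation.** SAEs, MAAEs and AESIs are collected to the D366 call (Protocol 8.3.2). SAP 5.1.3 ends the Treatment Period at loss to follow-up or withdrawal of consent.
- **Efficacy handling.** SAP 6.6.1 sets the end date equal to the start date for an infant with no safety contact at all.
- **Withdrawals.** SAP 6.6.2.2 warns that "an excess of withdrawals might be observed in the no intervention group" and answers with a tipping-point analysis, for efficacy only.
- **Immediate and related events.** Protocol 8.3.2 says "Participants enrolled in the nirsevimab group will be kept under observation for 30 minutes after immunization to ensure their safety". SAP 6.7.2.1 defines immediate AEs relative to immunization. It counts a missing relationship as related in dosed infants and as not related in controls. Both event types are nevertheless in the list of tables shown by arm and overall.

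**The concern.** The two halves of the SAP treat the same infant differently. For efficacy, an infant never contacted after Day 1 contributes almost no follow-up. For safety, that infant is a full member of the denominator with no events. If such infants are more common among controls, as the SAP allows, control AE percentages fall for reasons unrelated to health and nirsevimab looks worse. The opposite imbalance would hide harm. The Clopper-Pearson intervals describe sampling error only and cannot show either effect.

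The safety set also has a built-in asymmetry. An infant randomized to nirsevimab but not injected leaves it (SAP 6.7.2.2 provides a separate listing for such cases). A control whose family disengages straight after allocation stays in.

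Safety characterization is a secondary objective (Protocol Section 3), and the 12-month SAE, MAAE and AESI tables are its main controlled evidence.

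A second, simpler matter is the overall column for immediate and treatment-related TEAEs. It averages dosed infants with infants who received no product.

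**Working it through.** The plan states no AE rate and no loss rate, so there is no figure of its own to reproduce on this point. The only planned number used is the arm size: 28 860 / 2 = 14 430 (Protocol 9.2).

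**1. The same uncontacted infant under the two rules**

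- Efficacy (SAP 6.6.1): (end − start + 1) / 30.4375 with end = start gives 1 / 30.4375 = 0.033 person-months.
- Safety (SAP 6.7.2.2 with 6.1): 1 in the denominator, 0 in the numerator, for the full 12 months.

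**2. Effect of unequal loss on 12-month percentages**

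Assumptions: the same true AE hazard in both arms, constant over the year; loss at a constant rate, unrelated to AE risk. For true 12-month risk R and 12-month loss d:

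- λ = −ln(1 − R), g = −ln(1 − d)
- crude percentage = λ / (λ + g) × [1 − exp(−(λ + g))]

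Example with R = 10%, so λ = 0.1054:

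- Control, d = 10%: g = 0.1054; 0.5 × (1 − 0.90 × 0.90) = 9.50%.
- Nirsevimab, d = 2%: g = 0.0202; 0.839 × (1 − 0.90 × 0.98) = 9.90%.
- Ratio 9.90 / 9.50 = 1.042; the true ratio is 1.00.

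| True risk | Loss, nirsevimab / control | Nirsevimab | Control | Ratio |
|---|---|---|---|---|
| 2% | 2% / 5% | 1.98% | 1.95% | 1.016 |
| 2% | 5% / 20% | 1.95% | 1.79% | 1.087 |
| 10% | 2% / 5% | 9.90% | 9.75% | 1.015 |
| 10% | 2% / 10% | 9.90% | 9.50% | 1.042 |
| 10% | 5% / 20% | 9.75% | 8.98% | 1.086 |
| 35% | 2% / 5% | 34.67% | 34.18% | 1.014 |
| 35% | 5% / 20% | 34.18% | 31.62% | 1.081 |

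Upper bound: if all loss fell on Day 1, the ratio would be (1 − d_N) / (1 − d_C), that is 0.98 / 0.95 = 1.03 up to 0.95 / 0.80 = 1.19.

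30-day window: with 30-day risks of 10% or 30% and the same annual loss rates (2% vs 10%, 5% vs 20%), the ratio is 1.003 to 1.007.

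**3. What a person-time rate does in the example**

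Expected person-time is [1 − exp(−(λ + g))] / (λ + g).

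- Control: 0.190 / 0.2107 = 0.902 years; 0.0950 / 0.902 = 0.105 per year.
- Nirsevimab: 0.118 / 0.1256 = 0.940 years; 0.0990 / 0.940 = 0.105 per year.

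The ratio returns to 1.00, provided loss is unrelated to AE risk.

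**4. The overall column for immediate and related TEAEs**

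Overall = r × 14 430 / (14 430 + 14 430) = r / 2, where r is the rate in dosed infants. A rate of 1.0% shows as 0.50%, and 3.0% as 1.50%. Ten immediate events are 10 / 14 430 = 0.069% of dosed infants but 10 / 28 860 = 0.035% overall. The nirsevimab column shows r itself.

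**The case against.** The best defence is that crude percentages with exact intervals are a conventional, legitimate display for a single-dose product, and that SAP 6.7.2.2 rules out statistical comparison of AEs between arms. Loss is also actively limited. Under Protocol 7.3 nobody is deemed lost before the 12-month call (24-month for UK reconsented participants). Under the Schedule of Activities notes and Protocol 7.2, sites try to complete safety follow-up after early termination. An imbalance would be visible in disposition by arm (SAP 6.2), time to discontinuation (SAP 6.6.7.5) and monthly eDiary response (SAP 6.6.7.8). The shells may set other denominators. Dosed infants with no later contact also stay in the safety set, so most of any bias depends on an imbalance that may not occur. And an exposure-adjusted rate needs non-informative censoring, the assumption that SAP 6.6.2.2 itself questions.

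Most of this stands and keeps the point modest. It does not remove it. With no test planned, readers will compare the side-by-side percentages. The discontinuation displays would reveal an imbalance without correcting any AE figure. SAP 6.7 itself names no other denominator.

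Four stronger readings are tempting and not supported:

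- *The SAP expects more control withdrawals, and uses person-time for efficacy for that reason.* It says only that an excess might occur, gives no rate, and offers this as the reason for the tipping-point analysis.
- *By-arm immediate and related rates are distorted.* The nirsevimab column is right. The control cells are structural zeros for immediate AEs and effectively so for related ones.
- *Short follow-up at the Primary Analysis biases the comparison.* It lowers percentages in both arms alike under 1:1 randomization, and the First Year Analysis follows with complete data.
- *The spurious difference could reach about 4 standard errors.* With 30% risk and loss of 3% against 10%, that needs all loss on Day 1 (29.1% vs 27.0%). Spread over the year it is 29.6% vs 28.6%, ratio 1.04, about 1.9 standard errors.

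**Conclusion.** The point holds in limited form. The 12-month SAE, MAAE and AESI percentages treat unobserved time as event-free time, which the SAP does not do for efficacy. If control loss is higher, control percentages are understated and nirsevimab looks slightly worse. Under assumed losses of 2-5% against 5-20% spread over the year, the crude ratio is about 1.01 to 1.09 instead of 1.00; in the 30-day window the effect is negligible. These sizes rest wholly on assumed loss rates, equal constant hazards and loss unrelated to AE risk. The pooled-column point needs none of these assumptions: at 1:1 allocation, immediate and related TEAE percentages in the overall column are about half those in dosed infants. Neither point touches the confirmatory efficacy conclusions. The change is worth making because it is cheap and safety is a stated objective.

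**What to change.** In SAP 6.7.2.2:

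1. Beside the crude percentages, add by-arm exposure-adjusted incidence for 12-month SAEs, MAAEs and AESIs: infants with a first event, divided by person-months from Day 1 to first event, last safety contact or period end, with an exact Poisson interval. Use last safety contact and not the date of being declared lost, because Protocol 7.3 defers that declaration to the final call. State that the rate still assumes non-informative censoring.
2. Present immediate and treatment-related TEAEs for nirsevimab recipients, without a pooled overall column.

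Two extensions should be avoided. Limiting Day-31 tables to infants with a contact covering Day 31 or an earlier event would keep early losses with an event and drop those without, which conditions on the outcome. A 12-month exposure-adjusted rate for any TEAE would mix collection windows, because non-serious AEs are collected only to D31 (Protocol 8.3.2).

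No new data are needed: contact dates are already used to derive efficacy follow-up. The cost is SAP wording and slightly longer safety tables.

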9.5 Interim Analyses

A Primary Analysis is planned prior to the formal completion of the study. The efficacy analyses planned in the Primary Analysis will serve the purpose of evaluating the efficacy of nirsevimab in the study population. Efficacy data analyzed in the First Year and Second Year Analyses are exploratory therefore a multiplicity adjustment is not needed. These analyses will be conducted at the timepoints described in Section 9.4.1.

10 Supporting Documentation and Operational Considerations

10.1 Appendix: Regulatory, Ethical, and Study Oversight Considerations

Note: The term "participant" is used throughout this protocol. However, the term "subject" will be used in the eCRF in order to comply with the Clinical Data Interchange Standards Consortium (CDISC) requirements. Similarly, "legally acceptable representative" is used in the protocol whereas "guardian" is used in the eCRF.

10.1.1 Regulatory and Ethical Considerations

- This study will be conducted in accordance with the protocol and with the following:
 - Consensus ethical principles derived from international guidelines including the Declaration of Helsinki and Council for International Organizations of Medical Sciences (CIOMS) International Ethical Guidelines
 - Applicable ICH Good Clinical Practice (GCP) Guidelines

- Applicable laws and regulations (eg, data protection law as General Data Protection Regulation [GDPR])
- The protocol, informed consent form (ICF), Investigator Brochure (IB), and other relevant documents (eg, advertisements) must be submitted to an IRB/IEC by the investigator or the Sponsor (according to local regulations) and reviewed and approved by the IRB/IEC before the study is initiated
- Any amendments to the protocol will require IRB/IEC approval before implementation of changes made to the study design, except for changes necessary to eliminate an immediate hazard to study participants
- Protocols and any substantial amendments to the protocol will require health authority
 approval prior to initiation except for changes necessary to eliminate an immediate hazard to
 study participants.
- The investigator will be responsible for the following:
 - Providing written summaries of the status of the study to the IRB/IEC annually or more frequently in accordance with the requirements, policies, and procedures established by the IRB/IEC
 - Determining whether an incidental finding (as per Sanofi policy) should be returned to a
 participant and, if it meets the appropriate criteria, to ensure the finding is returned (an
 incidental finding is a previously undiagnosed medical condition that is discovered
 unintentionally and is unrelated to the aims of the study for which the tests are being
 performed). The following should be considered when determining the return of an
 incidental finding:
 - The return of such information to the study participant (and/or his/her designated healthcare professional, if so designated by the participant) is consistent with all applicable national, state, or regional laws and regulations in the country where the study is being conducted, and
 - The finding reveals a substantial risk of a serious health condition or has reproductive importance, AND has analytical validity, AND has clinical validity.
 - The participant in a clinical study has the right to opt out of being notified by the Investigator of such incidental findings. In the event that the participant has opted out of being notified and the finding has consequences for other individuals, eg, the finding relates to a communicable disease, Investigators should seek independent ethical advice before determining next steps.
 - In case the participant's parents or LARs have decided to opt out, the Investigator must record in the site medical files that she/he does not want to know about such findings.
 - Notifying the IRB/IEC of SAEs or other significant safety findings as required by IRB/IEC procedures

• Providing oversight of the conduct of the study at the site and adherence to requirements of 21 CFR, ICH guidelines, the IRB/IEC, European regulation 536/2014 for clinical studies (if applicable), European Medical Device Regulation 2017/745 for clinical device research (if applicable), and all other applicable local regulations

As applicable, according to Directive 2001/20/EC, the Sponsor will be responsible for obtaining approval from the Competent Authorities of the EU Member States and/or Ethics Committees, as appropriate, for any amendments to the clinical trial that are deemed as "substantial" (ie, changes which are likely to have a significant impact on the safety or physical or mental integrity of the clinical trial participants or on the scientific value of the trial) prior to their implementation.

